## **9.2 Patient demographics and other baseline characteristics**

### **9.2.1 Demographics and baseline characteristics**

Summary statistics will be presented for continuous demographic and baseline characteristic variables (including the baseline values of the secondary efficacy variables) for each treatment group and for all patients in the randomized set. The number and percentage of patients in each category will be presented for categorical variables for each treatment group and all patients.

Demographic and baseline disease characteristics will be summarized for the variables listed in [Section 6.2](#).

### **9.2.2 Medical history**

Relevant medical history (ocular and non-ocular) and current medical conditions will be tabulated by site (non-ocular, ocular (study/fellow eye)), system organ class (SOC) and preferred term of the MedDRA dictionary. Other relevant baseline information will be listed and summarized as appropriate with descriptive statistics. Analyses will be based on the Randomized Set.

## **9.3 Treatments**

### **9.3.1 Study treatment**

Descriptive statistics will be provided to characterize study treatment using the Safety Set.

The number of patients receiving ranibizumab injections and laser treatments will be presented in frequency tables and cumulatively by treatment group. Summaries will be presented for the study eye only and for all ranibizumab injections/laser treatments in both the study eye and the fellow treated eye as appropriate. Other data related to the treatment or application procedure will be summarized as appropriate.

### **9.3.2 Bilateral treatment**

The number of patients who received 3 or more injections of ranibizumab (study and fellow treated eye) within a  $30 \pm 7$  days period will also be summarized by treatment group within the Safety Set.

### **9.3.3 Prior and concomitant medication**

Prior and concomitant medications will be summarized in separate tables by treatment group.

Prior medications are defined as treatments taken and stopped prior to first dose of study treatment. Any medication given at least once between the day of first dose of randomized study treatment and the date of the last study visit will be a concomitant medication, including those which were started pre-baseline and continued into the period where study treatment is administered.

Tables will show the overall number and percentage of patients receiving at least one treatment of a particular ATC code and at least one treatment in a particular anatomical main group.

Significant prior and concomitant non-drug therapies and procedures will be summarized by primary system organ class and MedDRA preferred term using the Safety Set.

## **9.4 Analysis of the primary variable**

### **9.4.1 Variable**

The primary variable is the mean number of ranibizumab injections applied up to Month 11 between the 2 treatment arms in patients with visual impairment due to ME secondary to BRVO.

### **9.4.2 Statistical model, hypothesis, and method of analysis**

The primary analysis will be conducted at Month 12 within the FAS using observed data.

The following 1-sided hypothesis will be tested at the alpha level of 0.025:

$H_0: \mu_{\text{Ranibizumab-Laser}} - \mu_{\text{Ranibizumab-Mono}} = 0$  versus

$H_1: \mu_{\text{Ranibizumab-Laser}} - \mu_{\text{Ranibizumab-Mono}} \leq 0$

where  $\mu_{\text{Ranibizumab-Laser}}$  and  $\mu_{\text{Ranibizumab-Mono}}$  are the unknown mean values of the number of ranibizumab injections for the related treatment arms up to Month 11.

The statistical hypothesis testing of the number of ranibizumab treatments will be based on a stratified Cochran-Mantel-Haenszel (CMH) test. Stratification will be done based on categories of baseline decimal VA ( $<0.3$ , or  $\geq 0.3$ ). Difference of mean number of injections, 95% confidence interval (CI) of difference and one-sided p-value of the CMH test will be reported.

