#### Inclusion criteria for study eye

3. Diagnosis of visual impairment exclusively due to ME secondary to BRVO.
4. BCVA score at Screening and Baseline (Day 1) between 0.5 and 0.05 decimal (i.e., between 73 and 19 letters in ETDRS testing) with Landolt C charts inclusively (i.e., approximate logarithm of the minimum angle of resolution (logMAR) units of 0.3 to 1.30).
5. At Baseline (Day1), a maximum BCVA gain of 0.2 units logMAR conversion inclusively from screening is allowed as long as the BCVA score does not exceed the upper limit of 0.3 units logMAR.
6. Increased central subfoveal thickness ( $> 300 \mu\text{m}$  at Baseline (Day 1) when measured by SD-OCT)
7. Duration of vision deterioration  $\leq 6$  months (determined by self-report) at screening.

If both eyes are eligible, the one with the worse VA at screening will be selected as study eye, unless, based on medical reasons, the investigator deems the other eye to be more appropriate for treatment and study.

If the fellow eye presents with visual impairment due to ME secondary to RVO, it may also be treated with ranibizumab medication, laser photocoagulation or others and in line with the Japanese label and at the discretion of the investigator, however, any anti-VEGF treatments other than ranibizumab is not allowed. The fellow eye treated with ranibizumab is then labeled the fellow treated eye. Bilateral treatment with ranibizumab cannot be performed on the same day. Bilateral treatment indicates the number of patients who received 3 or more injections of ranibizumab (study and fellow treated eye) within a  $30 \pm 7$  days period.

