### **5.5.4.2 PRN (re-treatment/stabilization) criteria**

The PRN criteria for ranibizumab treatment is as detailed below:

After Baseline (Day 1) visit, if any one or more criteria from the below list is met, the patient should be considered for ranibizumab treatment (**re-treatment criteria**)

1. Center subfield thickness  $\geq 300 \mu\text{m}$
  2. An increase of CSFT  $\geq 20\%$  compare to minimum value during the treatment period
  3. The loss of VA due to disease activity secondary to BRVO (disease activity includes macular edema (ME), intra-retinal cysts, sub-retinal fluid, macular hemorrhage etc.). This criteria is based on Investigator's judgement including the following scenarios:
    - a. The VA is expected to improve if the existing disease activity is removed, hence investigator decides to treat with ranibizumab
    - b. The VA is expected to be decreasing because of the existing disease activity, hence investigator decides to treat with ranibizumab
    - c. The VA has decreased as compared to the previous month because of the appearance of disease activity, hence investigator decides to treat with ranibizumab (This criterion is to restart ranibizumab after interruption)
- If all the above criteria are not satisfied, then the patient should not be treated with ranibizumab (**stabilization criteria**), i.e.,
    1. Center subfield thickness  $< 300 \mu\text{m}$

2. An increase of CSFT < 20% compare to minimum value during the treatment period
3. VA is stable and the disease activity is in the state of not affecting VA (based on investigator's judgement).

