## **9.8 Sample size calculation**

In order to detect a clinically meaningful difference in the number of injections (at least 2 injections) at Month 11, as suggested by the principal investigators, this study will randomize at least 56 patients (28 per arm).

For the sample size calculation, we will assume a difference between arms of 2 injections and a standard deviation (SD) of 2.32 (based on CAVNAV study (Liegler et al. 2014)). Based on the non-parametric Wilcoxon-Mann Whitney test for the difference in means this would require 25 patients per arm with 80% power and a 0.025 significance level (1sided), however assuming approximate 10% drops out rate, a total of at least 56 patients (28 per arm) are required to be randomized.

Approximately 70 patients will need to be screened in order to have at least 56 patients eligible and commencing treatment in the trial.

All sample size calculations performed using EAST 6.0.

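### The primary comparison of injection counts is valid and reaches its stated power, but it leaves out baseline CSFT, a plausible predictor of the count that every eligible patient has on Day 1

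*Protocol*

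**What the plan says.** Protocol section 9.4.2 fixes the primary test: "The statistical hypothesis testing of the number of ranibizumab treatments will be based on a stratified Cochran-Mantel-Haenszel (CMH) test". It also fixes the factor: "Stratification will be done based on categories of baseline decimal VA", with a cut at 0.3. On the error rate it says "The following 1-sided hypothesis will be tested at the alpha level of 0.025". Section 5.3 balances randomization on the same VA split and on nothing else. Section 9.4.4 adds a per-protocol repeat and a possible stratified Wilcoxon-Mann-Whitney test, mentions CSFT in neither, and leaves any further analyses to the SAP.

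CSFT appears in two other places that bear on the count. In section 5.5.4.2 the first re-treatment criterion is "Center subfield thickness" of 300 µm or more. In section 4.1, criterion 6 requires "Increased central subfoveal thickness", above 300 µm on Day 1 by SD-OCT. I take the two terms to mean the same measurement.

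The sample size in section 9.8 rests on the unadjusted spread of the counts: "we will assume a difference between arms of 2 injections and a standard deviation (SD) of 2.32". This leads to 25 per arm for 80% power and, after 10% dropout, 28 per arm.

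**The concern.** An eye that enters well above 300 µm has further to fall before the first criterion stops calling for an injection. Baseline thickness may therefore explain part of the between-patient variation in the count. If it does, a comparison that ignores it leaves that variation in the error term and leaves any chance imbalance between arms in the estimate. Neither the randomization nor the analysis controls for it.

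This is the only comparison with a stated hypothesis and alpha level, and the planned minimum is 28 patients per arm. The value is already collected, so using it needs no extra visit or patient.

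**Working it through.** **Inputs.** From section 9.8: difference 2, SD 2.32, one-sided alpha 0.025, power 80%, Wilcoxon-Mann-Whitney test, 10% dropout. From section 9.4.2: a CMH test stratified by VA only. Assumed, because the protocol gives no figure: the within-arm correlation ρ between baseline CSFT and the count, taken over 0 to 0.5.

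**Step 1. Reproduce the planned size.** By Noether's formula, P(X<Y) = Φ(2 / (2.32 × √2)) = 0.729. Total N = (1.960 + 0.842)² / (12 × 0.25 × (0.729 − 0.5)²) = 49.92 with unrounded inputs, so 25 per arm. Then 25 / 0.9 = 27.8, so 28 per arm and 56 in total. The plan's figures are confirmed, and none of them relies on a covariate.

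**Step 2. Effect of adjustment by formula.** Adjustment multiplies the residual variance by 1 − ρ², so the SD becomes 2.32 × √(1 − ρ²). For n, I use 2 × (SD × 2.802 / 2)² / 0.864, where 0.864 is the lower bound for the efficiency of the Wilcoxon test relative to the t-test. At ρ = 0 this gives 21.12 / 0.864 = 24.4, again 25 per arm. Power at 25 per arm is Φ(2 / (SD × √(2 / 21.6)) − 1.960), where 21.6 = 25 × 0.864. The CI half-width is 2.011 × SD × √(2/25).

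| ρ (assumed) | 1 − ρ² | SD | n per arm for 80% | Power at 25 per arm | 95% CI half-width |
|---|---|---|---|---|---|
| 0 | 1.00 | 2.320 | 25 | 80.9% | 1.32 |
| 0.2 | 0.96 | 2.273 | 24 | 82.4% | 1.29 |
| 0.3 | 0.91 | 2.213 | 23 | 84.4% | 1.26 |
| 0.4 | 0.84 | 2.126 | 21 | 87.1% | 1.21 |
| 0.5 | 0.75 | 2.009 | 19 | 90.5% | 1.14 |

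**Step 3. Simulation of the tests themselves.** The settings were 25 per arm, 6,000 trials per setting, and counts rounded and limited to 1 to 12. Arm means before rounding were 6.5 and 4.5 (assumed). The VA stratum was given no effect.

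| ρ (assumed) | CMH by VA | Linear model: arm, VA stratum, continuous CSFT | Change in points | CMH by VA and median-split CSFT |
|---|---|---|---|---|
| 0 | 83.7% | 83.3% | −0.4 | 81.8% |
| 0.2 | 83.3% | 84.2% | about +1 | 82.4% |
| 0.3 | 83.6% | 86.4% | about +3 | 84.0% |
| 0.5 | 83.4% | 91.7% | about +8 | 87.5% |

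Under no difference between arms, rejection stayed between 0.022 and 0.026 for every option. The simulation error of one power figure is √(0.84 × 0.16 / 6000), about 0.5 points. The tests share the same simulated data, so their differences are steadier than that. The linear model here used ordinary standard errors; the robust ones recommended below were not part of this run.

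**Step 4. How CSFT enters matters.** As a second CMH stratum split at the median, CSFT costs about 2 points at ρ = 0 and about 1 at ρ = 0.2. Adding a further uninformative covariate also has a price. In a separate run (4,000 trials, 28 per arm, CMH test on residuals from CSFT and a non-prognostic second covariate), power at ρ = 0 went from 87.7% to 86.6%.

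**Step 5. Chance imbalance.** At 28 per arm, a one-standard-error imbalance in CSFT is √(2/28) = 0.27 SD. At ρ = 0.4 it moves the estimated difference by 0.27 × 0.4 × 2.32 = 0.25 injections, one eighth of the target of 2.

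**The case against.** The strongest defence is that nothing here is an error. The planned test uses the factor that balanced the randomization, holds its alpha, and reaches its stated power. Chance imbalance in CSFT is already covered by its error rate. Amendment 2 reports 59 patients randomized with enrollment ongoing, so 28 per arm is a floor. All of this stands.

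The second objection is that the gain depends on a correlation nobody has supplied. The trigger uses CSFT during the study, not at baseline, and every eye starts above 300 µm. The second criterion is relative to the patient's own minimum, and the third is investigator judgement on VA. Section 5.5.4.1 also does not recommend continued treatment after three injections without improvement, which could weaken a positive link between baseline thickness and the count. This stands as a limit on what can be claimed: the link is plausible, not shown. It does not remove the point, because the cost at zero correlation is about 0.4 points, against about 3 at 0.3 and 8 at 0.5.

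The third objection concerns credibility. The trial is open-label, patients have been randomized, and section 11.1 requires a written amendment for any protocol change. This also stands, and it is why the fix includes a route that leaves the primary test untouched.

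**Conclusion.** The omission is an efficiency choice that can be improved at low cost. Its likely value lies between nothing and about 8 points of power at 25 per arm for correlations from 0 to 0.5. In precision, the variance of the difference falls by 4% to 25% for correlations of 0.2 to 0.5, which takes the CI half-width from 1.32 to between 1.29 and 1.14 injections. These sizes rest on the assumed correlation and, for the simulated power, on the assumed arm means and count range.

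Three stronger readings are tempting, and the protocol supports none of them.
- A reader might infer that the primary test is invalid or underpowered. It is neither: the 25 per arm reproduces exactly.
- A reader might infer that the precision is free or certain. The protocol gives no correlation; the gain is negligible when it is weak, and a categorized CSFT stratum can lose power.
- A reader might infer that the reported p-value and CI conflict because section 9.4.2 does not say how the CI is computed. That method is ordinary SAP detail and is no defect in the protocol.

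**What to change.** Before database lock, pre-specify one linear model for the number of injections with arm, VA stratum and continuous baseline CSFT as the only terms, with robust standard errors of a named small-sample type. State that the covariate is the Day 1 value taken before first treatment, as used for criterion 6, because section 9 otherwise defines baseline as the last value before Day 1. Take the difference, its 95% CI and the one-sided p-value from this same model. Keep the planned stratified CMH test as a sensitivity analysis. Do not add CSFT as a second CMH stratum.

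If the sponsor will not change the primary test, name this model as the supportive analysis under section 9.4.4, which already allows further analyses to be set out in the SAP.

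The programming is small and no new data are needed. The statistical cost is a negligible loss of power if CSFT proves not prognostic. The procedural cost is larger for the first route: section 9.4.2 is protocol text, so changing the primary test needs a documented amendment with the approvals in section 11.1. Because the study is open-label, it must be dated before lock so that the choice cannot look data-driven. The supportive route needs only SAP text, signed off before lock.

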### **9.4.3 Handling of missing values/censoring/discontinuations**

No imputation is required for the primary endpoint which is number of ranibizumab injections, based on PRN regimen that is the number of injections during the study period will be used for the primary endpoint.

### **9.4.4 Sensitivity analyses**

For sensitivity purposes, the primary analysis will be repeated for the PPS population. Any major discrepancies in the results across analyses will be investigated as necessary.

The primary analysis may also be supported by using a stratified non-parametric Wilcoxon-Mann-Whitney test. Further analyses performed if any, will be provided in SAP.

## **9.5 Analysis of secondary variables**

### **9.5.1 Efficacy variables**

The following secondary efficacy endpoints will be evaluated for the study eye:

- The mean change in BCVA from Month 1 through Month 12 compared to Baseline (Day1) using decimal chart converted to be logMAR units, and ETDRS (Month 6, and Month 12) by both the treatment arms.
- The mean average change in BCVA from Month 1 through Month 12 compared to Baseline (Day1) using decimal chart converted to be logMAR units by both the treatment arms.
- The proportion of patients achieving BCVA improvement of  $\geq 5$ ,  $\geq 10$ ,  $\geq 15$ , and  $\geq 30$  letters and proportion of patients experiencing a loss of  $< 15$  letters from Baseline (Day1) to Month 12 by treatment arms.
- The proportion of patients reaching BCVA values  $\geq 73$ ,  $\geq 80$ , and  $\geq 85$  letters (approximate 0.5, 0.8, and 1.0 Decimal equivalent) at Month 12 by treatment arms.
- The mean change in CSFT from Month 1 through Month12 compared to Baseline (Day1) by the treatment arms.
- The mean average change in CSFT from Month 1 through Month12 compared to Baseline (Day1) by the treatment arms.

The analyses for the secondary endpoints are described below.

All endpoints relating to secondary objectives will also be summarized descriptively. Summary statistics will include relative and absolute frequencies for the categorical variables and the number of patients (N), minimum, mean, median and maximum for continuous variables. Further analyses, if required, will be described in SAP.

#### **9.5.1.1 BCVA from Month 1 through Month 12**

The mean change in BCVA from Month 1 through Month 12 will be compared to Baseline (Day1) using decimal chart and ETDRS (only at Baseline (Day1), Month 6, and Month 12) between the 2 treatment arms. The analyses at each visit will be based on an analysis of variance (ANOVA) model with treatment group, and stratification factors. Stratification will be done based on categories of baseline decimal VA ( $< 0.3$ , or  $\geq 0.3$ ). The Least Squares

Means (LS Means) estimates of BCVA compared to Baseline (Day1), difference of LS Means, their 95% confidence interval (CI) and the p-value (related to the null hypothesis that difference in mean change is zero) will be reported.

The mean average change in BCVA from Month 1 through Month 12 will also be compared to baseline characteristic to the above model using decimal chart converted to be logMAR units by both the treatment arms.

To obtain the mean average BCVA change from Month 1 through Month 12, the sum of single patient's average BCVA changes will be divided by the number of patients.

The average change in BCVA will be calculated for each single patient as follows:

$$\text{Average } \Delta \text{ BCVA} = \frac{\Delta \text{ BCVA}_{M1} + \Delta \text{ BCVA}_{M2} + \dots + \Delta \text{ BCVA}_{M12}}{12}$$

Where  $\Delta \text{ BCVA}_{Mx}$  = change in BCVA from Baseline (Day1) at Month x

The analyses will be conducted within the FAS using the LOCF approach.

Endpoints related to the number and proportion of patients with BCVA letter gain or loss from Baseline (Day1) will be analyzed via stratified CMH test with stratification factors as described above.

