## **5.3 Treatment assignment and randomization**

At Baseline (Day1) all eligible patients will be randomized via Interactive Response Technology (IRT) to one of the treatment arms. The investigator or his/her delegate will contact the IRT after confirming that the patient fulfills all the inclusion/exclusion criteria. The IRT will assign a randomization number to the patient, which will be used to link the patient to a treatment arm.

The randomization numbers will be generated using the following procedure to ensure that treatment assignment is unbiased and concealed from patients/subjects and investigator staff. A patient randomization list will be produced by the IRT provider using a validated system that automates the random assignment of patient numbers to randomization numbers. These randomization numbers are linked to the different treatment arms.

The randomization will be balanced by VA ( $0.3 <$ , or  $\geq 0.3$  assessed by decimal VA which is translated into 58 letters in EDTRS).

The randomization scheme for patients will be reviewed and approved by a member of the Biostatistics Quality Assurance (BQA) Group.

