#### **9.5.1.2 Central subfield thickness from Month 1 through Month 12**

The mean change in investigator-assessed CSFT from Month 1 through Month 12 will be compared to Baseline (Day1) by the treatment arms. The analyses at each visit will be based on an analysis of variance (ANOVA) model as analogous to BCVA.

The mean average change in investigator-assessed CSFT from Month 1 through Month 12 will also be compared to Baseline (Day1) analogous to the above model by both the treatment arms.

The analyses will be conducted within the FAS using the LOCF approach.

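### The BCVA and CSFT change models adjust only for a two-level baseline VA stratum, so CSFT change is not adjusted for baseline CSFT and can lose precision

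*Protocol*

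**What the plan says.** Section 9.5.1.1 of the protocol fixes the by-visit model for change in BCVA: "The analyses at each visit will be based on an analysis of variance (ANOVA) model with treatment group, and stratification factors". One factor is defined, baseline decimal VA in two classes (below 0.3, or 0.3 and above). Section 5.3 uses the same cut for randomization, "assessed by decimal VA which is translated into 58 letters in EDTRS".

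Section 9.5.1.2 has the CSFT change analysis "based on an analysis of variance (ANOVA) model as analogous to BCVA", and treats the mean average CSFT change the same way. No continuous baseline covariate is named for either endpoint.

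The mean average BCVA change "will also be compared to baseline characteristic to the above model". That sentence cannot be read with certainty as a model, so whether a baseline covariate was meant there is open. The point made here concerns the by-visit models.

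The baseline values exist. Inclusion criterion 6 requires CSFT above 300 µm "at Baseline (Day 1) when measured by SD-OCT". Criterion 4 requires BCVA "between 73 and 19 letters in ETDRS testing". Section 9.2.1 already summarizes baseline data, "including the baseline values of the secondary efficacy variables".

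**The concern.** A change score is follow-up minus baseline, so baseline variation that the model does not remove stays in the residual. For CSFT the model removes only what a VA class happens to explain. For BCVA it treats all eyes on one side of 58 letters alike, within an eligible range of 19 to 73. A chance baseline imbalance within strata is also left uncorrected.

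The trial sets out to show fewer injections without loss of efficacy, but the primary test covers only the injection count. BCVA and CSFT are the comparisons that show whether vision and anatomy hold up. They have no sample size calculation of their own and a planned 28 patients per arm. The width of their intervals decides how large a loss can be excluded.

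CSFT is the likelier problem. Baseline has a lower limit only, while in both arms CSFT of 300 µm or more is a re-treatment criterion in Section 5.5.4.2, with the converse "If all the above criteria are not satisfied, then the patient should not be treated with ranibizumab". That pulls follow-up toward a common level, so a follow-up spread no larger than the baseline spread is plausible. For BCVA, baseline is bounded on both sides and follow-up is not, which points the other way.

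**Working it through.** **Planned size.** The protocol gives no precision figure for BCVA or CSFT; its only calculation is for injections (Section 9.8). That one reproduces. For the Wilcoxon-Mann-Whitney test with difference 2 and SD 2.32, p = Φ(2/(2.32·√2)) = 0.729. The Noether formula gives (1.960 + 0.842)²/(3·0.229²) = 49.9 in total, so 25 per arm, and 25/0.9 = 27.8 gives 28 per arm.

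**Assumed inputs (not in the protocol).**
- ρ, baseline to follow-up correlation: 0.3, 0.5, 0.7.
- k, baseline SD divided by follow-up SD: 0.75, 1, 1.5.
- r, size of the VA–CSFT correlation: 0 to 0.5.

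**Formula.** Set the follow-up SD to 1. Regressing change on baseline leaves 1 − ρ². With the stratum alone, the baseline part (ρ − k)²(1 − R²) stays in as well, where R² is the share of baseline variance that the stratum explains. The stratum is taken to relate to follow-up only through baseline. With the stratum in both models:

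variance ratio = (1 − ρ²) / [(ρ − k)²(1 − R²) + 1 − ρ²]

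**R² for CSFT.** For a median cut on VA, R² = 2r²/π: 0 at r = 0 and 0.159 at r = 0.5.

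**R² for BCVA.** Take a uniform baseline over 19–73 letters cut at 58. The share above the cut is p = 15/54 = 0.278, and R² = 3p(1 − p) = 0.602. About 40% of baseline variance is left unadjusted.

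**Examples at k = 1, ρ = 0.5.**
- CSFT, r = 0: 0.75/(0.25 + 0.75) = 0.750.
- BCVA: 0.75/(0.25·0.398 + 0.75) = 0.883.

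**CI width.** The last two columns are mean 95% CI width with the covariate divided by width without it. They come from 6,000 simulated trials per setting with 28 per arm and allocation balanced within stratum, so they include the lost degree of freedom and chance imbalance.

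| Setting | Var. ratio, ρ=0.3 | ρ=0.5 | ρ=0.7 | CI ratio, ρ=0.3 | ρ=0.7 |
|---|---|---|---|---|---|
| CSFT, k=1.5, r=0 | 0.387 | 0.429 | 0.443 | 0.630 | 0.672 |
| CSFT, k=1.5, r=0.5 | 0.429 | 0.471 | 0.487 | 0.663 | 0.706 |
| CSFT, k=1, r=0 | 0.650 | 0.750 | 0.850 | 0.814 | 0.931 |
| CSFT, k=1, r=0.5 | 0.688 | 0.781 | 0.871 | 0.838 | 0.943 |
| CSFT, k=0.75, r=0 | 0.818 | 0.923 | 0.995 | 0.913 | 1.008 |
| CSFT, k=0.75, r=0.5 | 0.842 | 0.935 | 0.996 | 0.926 | 1.008 |
| BCVA, k=1 | 0.823 | 0.883 | 0.934 | 0.915 | 0.977 |
| BCVA, k=0.75 | 0.919 | 0.968 | 0.998 | 0.968 | 1.009 |

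A BCVA baseline cut at its median instead gives variance ratios of 0.837 to 0.940 at k = 1.

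**Reading the table.**
- CSFT at equal SDs: 28/0.943² = 31.5 and 28/0.814² = 42.3, so 28 per arm with the covariate are worth about 31 to 42 without it.
- Break-even: 1.009²/0.998 = 1.020. The term pays for itself once residual variance falls by more than about 2%.

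**Cross-check.** A separate simulation with 25 per arm, k = 1 and r = 0.3 gave ratios of the treatment-effect variance of 0.70, 0.76 and 0.86 at ρ = 0.3, 0.5 and 0.7. The formula gives 0.663, 0.761 and 0.857 before the cost of the extra term. At ρ = 0.9 the gain almost vanishes (0.97).

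**The case against.** - **Nothing is invalid.** An ANOVA on change with the randomization factor is a sound analysis. No margin, power target or decision rule is attached to BCVA or CSFT, so a narrower interval changes no pre-stated conclusion. This stands, and it limits the point to efficiency in secondary comparisons.
- **The SAP could settle it.** The protocol defers to the SAP only further details (Section 9) and further analyses (Section 9.5.1). The model, its terms, the LS means, CI and p-value are stated in the protocol itself. An SAP, not seen here, that added the term would be departing from that model.
- **An analogous CSFT model might mean adjustment for baseline CSFT.** No CSFT categories or CSFT covariate are defined anywhere, so this reading has no support in the text.
- **The SD ratio is a guess.** This is largely fair. The 300 µm entry limit also compresses baseline CSFT. Section 5.5.4.2 says treatment should be considered at the threshold, which is weaker than certain re-treatment. Poor responders can widen the follow-up spread. This is why the range reaches down to k = 0.75, where the gain can vanish.
- **The numbers per arm are out of date.** The Amendment 2 rationale reports 59 patients randomized with enrollment continuing, so about 30 per arm or more. This is correct, but the ratios barely change at 30 per arm.
- **The BCVA gain is small.** Agreed.

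**Conclusion.** The point holds as a matter of precision in secondary analyses. The stated CSFT models leave out baseline CSFT, and the by-visit BCVA model adjusts for its own baseline in two classes only. For CSFT, the interval with baseline added would be 6 to 19% narrower at equal SDs and 29 to 37% narrower if the baseline SD is 1.5 times the follow-up SD. At a ratio of 0.75 it would lie between 9% narrower and 1% wider. For BCVA the range is 2 to 9% narrower at equal SDs, and from 3% narrower to 1% wider at 0.75.

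All of this rests on the assumed correlations and SD ratios; the direction for CSFT rests on the entry limit and the re-treatment threshold. There is no bias, and the primary result and sample size are unaffected.

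**What to change.** In Section 9.5.1.2, add continuous baseline CSFT to the CSFT models. In Section 9.5.1.1, add continuous baseline BCVA on the scale being analysed (logMAR for decimal VA, letters for ETDRS). Keep treatment and the VA stratum in both, and apply the term to the by-visit and the mean average change.

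Use the same baseline value from which the change is calculated, and say which it is. Section 9 defines baseline as the last value before Day 1, while Sections 9.5.1.1 and 9.5.1.2 refer to Baseline (Day 1). Rewrite the sentence on the mean average BCVA change so that its model can be read.

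If only one change is made, baseline CSFT is the one that matters; the BCVA term is good practice with a small expected gain.

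The cost is one term in each of two sections and one rewritten sentence. There are no new data, and no patients are lost, since a change score already requires the baseline value. The downside is one degree of freedom per model, and an interval about 1% wider if baseline adds nothing beyond the stratum.
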